### **8.1.1 DEFINITION OF ADVERSE EVENTS (AE)**

An AE is any untoward medical occurrence in a patient or clinical investigation subject administered a pharmaceutical product and that does not necessarily have a causal relationship with this treatment. An AE can therefore be any unfavorable and unintended sign (including an abnormal laboratory finding), symptom, or disease temporally associated with the use of a medicinal (investigational) product, whether or not related to the medicinal (investigational) product (see the ICH guidance for Clinical Safety Data Management: Definitions and Standards for Expedited Reporting).

### **8.1.2 DEFINITION OF SERIOUS ADVERSE EVENTS (SAE)**

- Any untoward medical occurrence that at any dose:
- Results in death,

- Is life-threatening,
- Requires inpatient hospitalization or prolongation of existing hospitalization,
- Results in persistent or significant disability/incapacity, or
- Is a congenital anomaly/birth defect.

#### 8.1.3 DEFINITION OF UNANTICIPATED PROBLEMS (UP)

Unanticipated problems include any incident, experience, or outcome that meets all of the following criteria:

- 1) unexpected (in terms of nature, severity, or frequency) given (a) the research procedures that are described in the protocol-related documents, such as the IRB-approved research protocol and informed consent document; and (b) the characteristics of the subject population being studied;
- 2) related or possibly related to participation in the research (in this guidance document, possibly related means there is a reasonable possibility that the incident, experience, or outcome may have been caused by the procedures involved in the research); and
- 3) suggests that the research places subjects or others at a greater risk of harm (including physical, psychological, economic, or social harm) than was previously known or recognized.

### 8.2 CLASSIFICATION OF AN ADVERSE EVENT

#### 8.2.1 SEVERITY OF EVENT

Classifications often include the following:

- **Mild:** Awareness of signs or symptoms, but easily tolerated and are of minor irritant type causing no loss of time from normal activities. Symptoms do not require therapy or a medical evaluation; signs and symptoms are transient.
- **Moderate:** Events introduce a low level of inconvenience or concern to the participant and may interfere with daily activities, but are usually improved by simple therapeutic measures; moderate experiences may cause some interference with functioning
- **Severe:** Events interrupt the participant's normal daily activities and generally require systemic drug therapy or other treatment; they are usually incapacitating

Severity is not synonymous with seriousness. A severe rash is not likely to be an SAE. Likewise, a severe headache is not necessarily an SAE. However, mild chest pain may result in a day's hospitalization and thus is an SAE.

#### 8.2.2 RELATIONSHIP TO STUDY AGENT

Adverse events may be caused by one or more of the following:

1. the procedures involved in the research;
2. an underlying disease, disorder, or condition of the subject; or
3. other circumstances unrelated to either the research or any underlying disease, disorder, or condition of the subject.

In general, adverse events that are determined to be at least partially caused by (1) would be considered related to participation in the research, whereas adverse events determined to be solely caused by (2) or (3) would be considered unrelated to participation in the research.

#### 8.2.3 EXPECTEDNESS

AEs must be assessed as to whether they were expected to occur or unexpected, meaning not anticipated based on current knowledge found in the protocol, investigator brochure, product insert, or label. Categories are:

- **Unexpected** - nature or severity of the event is not consistent with information about the condition under study or intervention in the protocol, consent form, product brochure, or investigator brochure.

- **Expected** - event is known to be associated with the intervention or condition under study.

#### Relatedness

The potential event relationship to the study intervention and/or participation is assessed by the site investigator. A comprehensive scale in common use to categorize an event is:

- *Definitely Related*: The adverse event is clearly related to the investigational agent/procedure – i.e. an event that follows a reasonable temporal sequence from administration of the study intervention, follows a known or expected response pattern to the suspected intervention, that is confirmed by improvement on stopping and reappearance of the event on repeated exposure and that could not be reasonably explained by the known characteristics of the subject's clinical state.
- *Possibly Related*: An adverse event that follows a reasonable temporal sequence from administration of the study intervention follows a known or expected response pattern to the suspected intervention, but that could readily have been produced by a number of other factors.
- *Not Related*: The adverse event is clearly not related to the investigational agent/procedure. - i.e. another cause of the event is most plausible; and/or a clinically plausible temporal sequence is inconsistent with the onset of the event and the study intervention and/or a causal relationship is considered biologically implausible.

Mild sunburns, not requiring medical treatment, are expected to be over reported in the treatment group because of their constant communication with the application. These will not be considered AE's for the purposes of the safety endpoint.

### 8.3 TIME PERIOD AND FREQUENCY FOR EVENT ASSESSMENT AND FOLLOW-UP

Adverse events reported will be assessed and followed up as soon as practical. Subjects reporting adverse events will be contacted by the study coordinator to schedule an assessment. Follow up timing will be sufficient to meet the following reporting requirements.

#### Unexpected fatal or life-threatening suspected adverse reaction reports:

The sponsor (or sponsor-investigator) must notify the FDA of any unexpected fatal or life-threatening suspected adverse reaction as soon as possible but no later than 7 calendar days after the initial receipt of the information.

#### Other reporting requirements:

The sponsor (or sponsor-investigator) must also notify the FDA and all participating Principal Investigators (in multi-site studies) in an safety report about potential serious risks, from clinical trials and any other source, no later than 15 days in the following cases:

- *Serious and unexpected suspected adverse reactions*. Any suspected adverse reaction that is both serious and unexpected must be reported. The report must proceed only if there is evidence to suggest a causal relationship between the drug and the adverse event.
- *Finding from other studies*. Any findings from epidemiological studies, pooled analysis of multiple studies, or clinical studies (other than those reported under serious and unexpected adverse reactions above) must be reported whether or not conducted under an IND or whether or not conducted by the investigator, that suggest a significant risk in humans exposed to the drug.
- *Increased rate of occurrence of serious suspected adverse reactions*. Any clinically important increase in the rate of serious suspected adverse reactions over that listed in the protocol must also be reported.

### 8.4 REPORTING PROCEDURES

#### **8.4.1 ADVERSE EVENT REPORTING**

If any medical event reaches the threshold of an adverse event (AE) as judged by a treating physician, the AE will be reported by study staff or medical staff within 24 hours using both email and telephone to the clinical PI, the study PI and the IRB.

Appropriate action will be taken by the clinical PI and reported in writing to Shade and the IRB within 72 hours.

A written summary of any Adverse Events and their disposition will be submitted by the study PI ([name]) to the funding NIH I/C within two weeks of receiving the written disposition from the clinical PI.

#### **8.4.2 SERIOUS ADVERSE EVENT REPORTING**

As in 8.4.1

#### **8.4.3 UNANTICIPATED PROBLEM REPORTING**

Unanticipated problems with the device or application will be reported to the study coordinator who will relay the reports to Sponsor. These will be managed by the sponsor using their process for Corrective and Preventive Actions. If a device is lost or becomes inoperable, a new device will be shipped to the subject by the study coordinator. Sponsor and study coordinator will communicate regularly about the inventory of devices and resupply as needed.

#### **8.4.4 EVENTS OF SPECIAL INTEREST**

The study team has not defined any events of special interest.

#### **8.4.5 REPORTING OF PREGNANCY**

Pregnancy will be noted on the CRF as a change in health status. Pregnancy will not result in exclusion from the study.

### **8.5 STUDY HALTING RULES**

The study can be halted at the request of the sponsor, the funding organization, the principal investigator or the IRB. It is expected that the study would be halted in the event that one or more of these reach the conclusion that as result of reported AE's it is unethical to continue the study.

### **8.6 SAFETY OVERSIGHT**

Study staff will record all visits (regularly scheduled and others) and any hospitalization events.

#### ***Safety Monitoring***

a. Adverse events: If any medical event reaches the threshold of an adverse event (AE) it will be reported and handled as described in 8.4.1.

b. Overall rates of hospitalization and occurrence of AK will be reported by Shade to the clinical PI and the IRB every six months until the study closes.

c. Final rates of hospitalization and occurrences of AK will be included in the final study report.

d. The Shade device does not require an FDA issued IDE. Shade, in consultation with its legal consultants, has determined that is a non-significant risk device because it is not an implant, is not used to sustain human life and is not used in the diagnosis or treatment of disease, and does not otherwise present a significant health risk. As such the device is subject to abbreviated requirements under 21 CFR 812.2(b)

- It will only be used in at risk-populations with IRB approval including monitoring and consent.
- The devices will be labeled 'Investigational Use Only'
- All FDA requirements concerning data reporting, monitoring and promotion will be observed. Shade will request an IRB determination that the device is not significant risk prior to the submission of the study protocol.

Shade may also request an FDA determination of non-significant risk prior to initiation of this study.

## **9 CLINICAL MONITORING**

All clinical data will be recorded on CRFs and monitored by a representative of Shade who may be an employee or an external study consultant. Monitors will perform source-data verification prior to study analysis. The data monitor will ensure that subject confidentiality is not breached by reviewing each CRF for the presence of identifying information. Monitoring visits will be held within two weeks of the first day of scheduled subject visits and continue periodically at the discretion of the sponsor but in no case less than at six month intervals until study closeout. To facilitate an orderly and timely analysis and to avoid an accumulation of data queries at closeout, there will be a monitoring visit four to six weeks before the end of data collection. At the conclusion of each monitoring visit a report indicating any issues with data, outstanding queries or protocol compliance issues. This report will be shared with Shade and the clinical PI. The results of monitoring visits and queries will be made available to the funding agency's project officer.

## **10 STATISTICAL CONSIDERATIONS**

### ***10.1 STATISTICAL AND ANALYTICAL PLANS***

The statistical analysis of the study is the responsibility of the study statistician. Intermediate data reviews will be conducted after 6 months to check for potential problems with data integrity.

### ***10.2 STATISTICAL HYPOTHESES***

The general hypothesis is that sun damage will be lower in the treatment group. The null hypothesis is that sun damage is the same or higher. Below there is a more precise statement of the hypothesis for each study aim.

### ***10.3 ANALYSIS DATASETS***

Datasets will be prepared by the study coordinator from case report forms. The tables will be formatted as requested by the study statistician and will be monitored.

### ***10.4 DESCRIPTION OF STATISTICAL METHODS***

Actinic keratosis (AK) is a frequent pre-cancerous skin lesion caused by damage from ultraviolet exposure. Without treatment, 1-2% of these lesions evolve into squamous cell carcinoma (SCC). Therefore, the number of AKs reflects the effect of UV exposure and the risk for SCC. Transplant patients are at high risk of skin cancer because of their immunosuppressive medications required to prevent organ rejection. Morbidity/mortality of SCC in this patient population can be as high as 25%.

The primary outcome of this trial will be a statistically significant reduction by at least 25% in the cumulative number of newly developed AK lesions between the control and the study group.

AK lesions on sun exposed skin areas (scalp, face, hands) will be counted and reported by dermatologists at enrollment and at each subsequent visit. AKs are defined as keratotic macule(s) or papule(s) on an erythematous base by dermatological examination. In addition to the enrollment visit, this study will include a follow up dermatological visit after the summer. For each patient, the number of newly occurred AKs will correspond to the cumulative AK counts during the study period. To insure that only new occurrences of AK lesions after V1 will be counted, data from subsequent study visits will include the location of AK lesions and pictures of the lesions.

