## PROTOCOL SUMMARY

Title:	Validation of shade, a wearable ultraviolet light monitor, for reduction of actinic keratosis
Summary:	
The incidence of non-melanoma skin cancers, due to increased ultraviolet (UV) exposure, has increased by 300% over the past 2 decades. The innovative UV sensor, Shade, is designed to help people manage their UV exposure by quantifying their UV exposure levels through a linked smartphone application. In order to validate the effectiveness of Shade, we propose conducting a study communicating the level of UV exposure and correlating it with the development of actinic keratosis (AK), a precancerous lesion of the skin. We will recruit patients with multiple AKs. We will include renal transplant patients as this population develop AKs as well. We will evaluate the UV monitor's effectiveness in decreasing the number of AKs over a summer. This randomized partially blinded study will recruit 120 patients with a recent history of AKs and evaluate the incidence of new AKs after one summer. We will perform a control versus study group analysis. Half of the subjects (study group) will be randomly assigned to use the sensor along with its smartphone application, while the other half (control group) will receive standard of care treatment involving counseling to avoid sun exposure. Subjects will have regular standard of care visits with the dermatologist who will follow the number of actinic keratosis via clinical exam and photography. The primary outcome will be a statistically significant reduction by at least 25% of the cumulative number of newly occurred AK lesions between the control and the study group over one summer, counted at enrollment and follow-up. In subjects at one study site, skin DNA damage will also be assessed using cyclobutane pyrimidine dimers (CPD) levels measured by ELISA in both sun exposed (nose) and sun protected skin (buccal mucosa) in both the study and control groups. Secondary outcomes will look at clinical decreases by 25% in CPD levels after using the sensor.

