#### 10.4.1 GENERAL APPROACH

All tests will be two-tailed with the significance level set at 0.05. Analysis will be performed using STATA statistical software (StataCorp. 2015) or R (R: A language and environment for statistical computing. R Foundation for Statistical Computing, Vienna, Austria).

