#### 10.4.2 ANALYSIS OF THE PRIMARY EFFICACY ENDPOINT(S)

##### **#1 (Primary): Quantify the impact of Shade on the cumulative number of new actinic keratoses developed over the study period.**

To test our primary aim, we will perform a control versus study group analysis. The study group will receive a Shade sensor and Shade app while the control group will standard of care sun avoidance counseling. The study will be randomized and single-blinded as described in section 10.6.1. This will also allow us to control for the effect of UV level variation on the primary outcome since the two groups will have balanced enrollment dates. All the patients will receive recommendations about UV exposure protection as defined by the recommendations of the American Academy of Dermatology and the National Cancer Institute.

Patients who will have used the Shade sensor for less than 15% of the days over the study period will be excluded from these analyses. We will use a Student's t-test with the following null and alternative hypothesis:

$$H_0: \text{mean}^C_{t12} (\text{AK}) = \text{mean}^I_{t12} (\text{AK})$$

$$H_a: \text{mean}^C_{t12} (\text{AK}) \neq \text{mean}^I_{t12} (\text{AK})$$

where  $\text{mean}^C_{t12} (\text{AK})$  is the averaged cumulative number of AK between enrollment follow up of controls and  $\text{mean}^I_{t12} (\text{AK})$  is the averaged cumulative number of AK of intervention patients.

In this analysis, demographic and clinical factors such as gender, age, baseline count of AKs, skin type, immunosuppressive treatment and comorbidity can be confounding factors. To test and control for confounding, demographic and clinical data (skin type, living area, gender, age, count of AK at enrollment, immunosuppressive (IS) treatment, level of immunosuppression and comorbidity) will be collected. We will use a stepwise multivariate approach with backward selection: 1) the effect of potential confounding factors will be tested using the same statistical tests, 2) factors with p-value <0.2 and less than 25% of missing values will be included in the multivariate model and 3) only covariates with significant adjusted p-value (<0.05) will be kept in the final model. Clinically relevant interactions will also be tested (e.g. skin type, gender, age) and kept in the final model if significant. The adjusted effect of Shade use will be estimated using a multivariate linear regression.

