### 10.5 SAMPLE SIZE

The most efficient approach to performing the power calculation for this study via Monte Carlo simulation as the underlying phenomenon, AK rate, is best modeled by a Poisson distribution.

As a starting point, we took the distribution of AK rates from actual clinical data. The data were assembled by querying EPIC on 2014 visits of kidney transplant patients to dermatology (this subset of the population will have fewer AK's than the non-transplant subjects and therefore use of this distribution will err on the side of caution toward overpowered the study). For each visit in which the dermatologist chose to treat by LN2 destruction, the query retrieved the number of procedures performed. This approach is conservative as the input data potentially underestimates AK count as some AK's may not have been treated.

The structure of the Monte Carlo was straightforward. A set of potential study sizes (N recruited) and effect sizes were chosen. For each input condition, two thousand random experiments were performed. In each of these interactions, baseline AK rates were drawn from the clinically observed distribution of AK's. Subjects were sequentially assigned to treatment or control groups. Observed AK rates were generated using a Poisson distribution for each visit. The analysis expected for the study was then performed. In this analysis the total count of AK's for each subject was obtained and the means and distributions compared for directionality (AK\_treated < AK\_control) and significance (p-value from a one-tailed t-test).

Analysis was performed in R (R Open 3.2.3) with statistical calculations and random number generation using the base and stat libraries.

[figure not shown]

Figure 10.5.1. With an effect size of 0.25 and recruitment of 100 patients (50 treatment, 50 control) we predict a power of 0.81.

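### The primary outcome is worded as a significant reduction of at least 25%, but neither the test in 10.4.2 nor the 0.81 power in 10.5 carries a 25% condition

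*Combined protocol and SAP*

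**What the plan says.** The Protocol Summary reads: "The primary outcome will be a statistically significant reduction by at least 25% of the cumulative number of newly occurred AK lesions". Section 10.4 repeats it: the outcome "will be a statistically significant reduction by at least 25% in the cumulative number of newly developed AK lesions". Section 4.2.1 names the endpoint without a threshold.

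Section 10.2 gives a directional null without a margin and adds: "Below there is a more precise statement of the hypothesis for each study aim". For aim #1, section 10.4.2 then says: "We will use a Student's t-test with the following null and alternative hypothesis". The null is equal mean cumulative AK counts and the alternative is unequal means. Section 10.4.1 sets the level: "All tests will be two-tailed with the significance level set at 0.05".

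In the simulation of section 10.5, each trial's total counts were analysed with "the means and distributions compared for directionality" and for significance by a one-tailed t-test. The result is: "With an effect size of 0.25 and recruitment of 100 patients (50 treatment, 50 control) we predict a power of 0.81". Planned recruitment is 120.

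The 25% wording recurs in section 10.4.3 for secondary endpoints #3, #4 and #7.

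**The concern.** A trial can reject the null in 10.4.2 and still miss the outcome as worded in the Summary and 10.4, for example with p<0.05 and an observed reduction of 20%. The plan does not say which statement decides. Results in that region are plausible on its own sources: section 2.2 cites differences of 11% to 20% in the nicotinamide trial on which the protocol is modelled, against 24% to 44% for sunscreen in section 2.1. Section 3 says the data will support the proposed indications for use, so the definition of success matters.

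The quoted power is also at stake. A reader of 10.4 and 10.5 together would take 0.81 as the chance of meeting the primary outcome at a true 25% reduction. That holds only if the outcome has no 25% condition.

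**Working it through.** **Inputs.** From 10.5: effect 0.25, 50 per arm, one-tailed t-test, power 0.81. From 10.4.1: two-sided 0.05. From 4.1: N=120, so 60 per arm. The mean and spread of AK counts are not given, so 0.81 cannot be reproduced independently. I solved for the spread that it implies.

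**Calibration to 0.81 (normal approximation).** Let s be the common SD as a fraction of the control mean. Power is Φ(0.25/(s√(2/n)) − 1.645). Setting this to 0.81 (z = 0.878) at n = 50 gives s = 0.25/(0.2 × 2.523) = 0.495.

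**Rule A: significance only, two-sided, true 25% reduction.**
- n = 50: SE = 0.495 × √(2/50) = 0.099. Power = Φ(0.25/0.099 − 1.96) = 0.71. Smallest significant reduction = 1.96 × 0.099 = 19%.
- n = 60: SE = 0.495 × √(2/60) = 0.0904. Power = Φ(0.25/0.0904 − 1.96) = 0.79. Smallest significant reduction = 18%.

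(The fall from 0.81 to 0.71 at 50 per arm reflects one-tailed against two-tailed testing, which is a separate matter.)

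**Rule B: significance and an observed reduction of at least 25%.** The second condition is T̄ − 0.75·C̄ ≤ 0, where T̄ and C̄ are the arm means. At a true 25% reduction the left side has expectation zero, so the condition is met with probability about 0.50 whatever the sample size. Adding the significance requirement can only lower this.

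**Share of trials in which A and B disagree.** This is A minus B: 0.79 − 0.50 = 0.29 at n = 60, and 0.71 − 0.50 = 0.21 at n = 50.

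**Simulation check.** Assumed: gamma-Poisson counts, pooled t-test, control means 4, 10 and 20, equal arms, no exclusions or dropout. Calibration to 0.81 gives total CV 0.53 to 0.56. Ranges are over the three means.

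| Setting | Rule A | Rule B | Disagree |
|---|---|---|---|
| N=100, true 25% | 0.71–0.72 | 0.50–0.51 | 0.21 |
| N=120, true 25% | 0.79 | 0.50 | 0.28–0.29 |
| N=120, true 20% | 0.57–0.58 | 0.26–0.27 | 0.31 |

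At 45 per arm and a true 25%, disagreement is about 0.16. At N=400, Rule B is still 0.50 to 0.51.

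**Sensitivity to the unstated spread (N=120, true 25%).** Disagreement is 0.33–0.36 at CV 0.50, 0.19–0.22 at 0.60, 0.07–0.10 at 0.70, 0.01–0.02 at 0.80 and 0 at 1.00. At CV 0.80 and above, a result must show roughly a 25% reduction to be significant at all (median boundary 26% at CV 0.80), so the two rules nearly coincide. Rule B falls to 0.45–0.46 at CV 0.80 and 0.33 at CV 1.00, but Rule A is then about 0.48 and 0.33. That loss is low power and not an effect of the 25% condition.

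**The case against.** The strongest reply is that nothing conflicts. The Summary and 10.4 have two parts, significance and size, and 10.4.2 specifies the test for the first without denying the second. The plan uses that pattern elsewhere: for PROMIS (endpoint #8) it judges statistical significance and then a 3-point change, and section 2.3.2 treats 25% as the result to be demonstrated. This stands as a fair reading. But on it 10.4.2 omits half of the success rule, and 0.81 describes only the other half.

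The opposite reply is that 25% is plainly the design effect. Sections 10.2, 10.4.2 and 10.5 favour that, but 10.4 is itself in the statistics chapter, below 10.2, so it is not merely loose summary wording.

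The reply on materiality also stands in part. Section 10.4.2 excludes sensor use below 15% of days, and 5.4.2 analyses complete data only, so fewer than 60 per arm may be analysed. Section 10.5 does not say how many visits were simulated, and 17.2 removed visits. If more visits were simulated than are now planned, the relevant CV is higher and disagreement is rarer.

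A reader might also infer that 25% is a margin to be tested, given the wording for #3 and #4. No null hypothesis with a margin appears anywhere, and aim #1 states equality, so the documents do not support that.

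**Conclusion.** The concern holds as a mismatch between the stated success rule and the stated power. On the literal wording, 0.81 is not the power of the rule, and about 0.50 is close to the ceiling at a true 25% reduction. That result needs almost no modelling. On the design-effect reading, 0.81 can stand as a one-tailed figure, and the Summary and 10.4 are misworded.

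How often the two rules would give different verdicts is uncertain. It is about 0.29 at N=120 and 0.21 at N=100 under the calibrated gamma-Poisson model without losses, about 0.16 at 45 per arm, and almost nil at CV 0.80 or more.

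A reader might go further and conclude that 0.81 is miscalculated, or that the sponsor has left room to choose a rule after seeing the data. The documents support neither. The simulation's scoring is described openly, 10.4.2 prespecifies the hypotheses, and 10.6.3 freezes the data tables before the blind is broken. The point should be fixed, and the repair is small.

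**What to change.** Before the blind is broken, state one rule in the Protocol Summary, 10.4 and 10.4.2.

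**Option 1.** *Primary success is a two-sided p<0.05 in favour of Shade in the Student's t-test of 10.4.2; 25% is the design effect used in 10.5, not a success threshold.* Record that the change was made after enrolment began and while blinded. Section 17.2 shows that some subjects had already completed visit 2 at an earlier protocol change, and on the literal reading this option loosens the rule.

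**Option 2.** Keep the 25% condition, which is a legitimate choice. Add it to 10.4.2 as a second condition on the observed reduction, rerun the 10.5 simulation with that rule on the sponsor's own AK distribution, and give the resulting probability of success in place of 0.81.

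Under either option, report the mean difference with its 95% CI. For the AK endpoint, also report the percentage reduction with a 95% CI by a named method, such as bootstrap or delta method, because the t-test yields only an absolute difference. Align the 25% wording for #3, #4 and #7 with the chosen option. Do not require a percentage-reduction CI for squamous cell carcinoma or nonmelanoma skin cancer counts, which may be sparse.

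**Cost.** No change to the test, alpha, sample size or data collection. The sponsor either gives up 25% as a success condition or states a lower probability of success, and needs one extra interval method.
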